6.3 Exclusion Criteria

Subjects enrolled in this study must not meet the following exclusion criteria, as determined by the Investigator:

1. Subject is unable to operate the system.
2. Subject is an unsuitable surgical candidate.
3. Subject has a condition currently requiring or likely to require the use of diathermy.
4. Subject has another implantable stimulator such as demand type pacemakers or cardioverter defibrillator.
5. Subject is <18 years old.
6. Subject is pregnant or nursing.
7. Subject is allergic, or has shown hypersensitivity, to any materials of the neurostimulation system which come in contact with the body.
8. Subject is involved in an injury claim under current litigation or has pending/approved worker's compensation claim.
9. Subject has prior experience with SCS.
10. Subject is being treated with electroconvulsive therapy (ECT) or transcranial magnetic stimulation (rTMS).

7 STUDY ASSESSMENTS

7.1 Study Pain Assessment

The Study Pain Assessment includes the following:

- A body map drawing for subjects to shade in the areas of the subject's pain that are intended to be treated with SCS (i.e., "study pain"). The Investigator will review the pain map with the subject and identify which are the pain locations intended to be treated with SCS and which are not.
- A Visual Analogue Scale (VAS) to rate study pain intensity for each region shaded as having study pain on the body map. The VAS consists of a 10 cm line with two end-points representing "no pain" and "worst pain imaginable". Subjects are asked to rate their pain by placing a mark

on the line corresponding to their level of pain. The distance along the line from the “no pain” end to the subject’s mark is measured.

- Questions regarding the quality and nature of the subjects’ study pain and sleep.
- At Baseline only:
 - Douleur Neuropathique 4 Questions (DN4), which is a screening tool for neuropathic pain with 10 items split across four questions regarding the subjects’ study indication pain. Seven items related to pain quality (i.e. sensory and pain descriptors) are based on an interview with the patient and 3 items are based on the clinical examination.
 - Questions regarding the study pain etiology and pathophysiology.

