6.2 Inclusion Criteria

Subjects enrolled in this study must meet the following inclusion criteria, as determined by the Investigator:

1. Subject has chronic intractable pain of the trunk and/or limbs (VAS ≥ 6 cm in at least one of the regions intended to be treated with SCS).
2. Subject is willing and capable of giving informed consent and able to comply with study-related requirements, procedures, and visits.
3. Subject has trunk and/or limb pain such that lead placement will be in the lumbar to cervical region.

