8.6 Follow-up Visits

Subjects will be followed-up at 1 month (30, -14 days, +21 days), 3 months (90±21 days), 6 months (180±30 days), 12 months (365±60 days), 18 months (545±90 days), 24 months (730±90 days). Subjects may have their device reprogrammed throughout follow-up. The following data will be collected during follow-up:

- Study Pain Assessment
- PROMIS-29+2
- PROMIS-10 Global
- POMS 2-A Short
PGIC & Patient Satisfaction
- Stimulation characteristics
- Posture change measurements
- Neurophysiologic measurements
- Device programming (as needed)

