13.5.1 Pain Assessment Training

Despite having validated methods for collecting pain measures, chronic pain clinical studies have been plagued by large variability in subjects' perception of pain and inconsistent reporting of these measurements. For example, a subject may give substantially differing pain scores at different follow-up time points but describe their pain as not having changed. For this reason, subject and Investigator/investigation site staff training on properly completing pain assessments will be performed to provide reliable and useful data. The training is two-fold, 1) train on the scale being used, and 2) train on the pain that is intended to be treated with SCS (to set expectations appropriately). As described by IMMPACT recommendations (26), this protocol requires Investigators (preferably the implanting Investigators) to perform a thorough training with the potential subject as part of the baseline assessment to set and manage appropriate expectations and increase subject understanding of the study indication pain (i.e., pain intended to be treated with SCS), as well as, differentiate comorbid pain conditions (non-index/non-study indication pain) to increase the likelihood of conscientious subject reporting of pain that is intended to be treated in the study. To obtain accurate reporting at follow-up, re-training will utilize the baseline pain map to remind the subject of the pain identified at baseline in which the Investigator intended to treat. Re-training of subjects on the proper completion of pain assessments to provide reliable and useful data may be conducted at any time during the study as the Investigator and site staff deem necessary.

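### Nothing fixes the follow-up VAS regions to the baseline map, so a fully relieved region may get no score and change from baseline may not compare the same regions

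*Combined protocol and SAP*

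**What the plan says.** Section 7.1 builds the Study Pain Assessment from a map and a scale. The map is "A body map drawing for subjects to shade in the areas of the subject's pain that are intended to be treated with SCS", and the Investigator goes over it with the subject to separate the locations SCS is meant to treat from the others. The scale is "A Visual Analogue Scale (VAS) to rate study pain intensity for each region shaded as having study pain on the body map", a 10 cm line whose lower end stands for no pain.

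The items that 7.1 lists under "At Baseline only" are the DN4 and the questions on etiology and pathophysiology. The map and the VAS are not among them. Table 4 and sections 8.4 and 8.6 schedule the Study Pain Assessment at Trial End and at 1, 3, 6, 12, 18 and 24 months.

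Section 13.5.1 brings the baseline map into follow-up: "re-training will utilize the baseline pain map to remind the subject of the pain identified at baseline". The next sentence says that re-training "may be conducted at any time during the study as the Investigator and site staff deem necessary".

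Section 6.2 makes the regional VAS the pain entry criterion: "VAS ≥ 6 cm in at least one of the regions intended to be treated with SCS". Sections 11.2 and 11.3 name no VAS endpoint, give no rule for combining regional scores within a subject, and set no responder threshold. They provide for summary statistics and one-sample t-tests, with repeated-measures and GEE analyses as possible additions.

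**The concern.** The VAS is tied to shading, and the shading shows where the subject has study pain. If the map is shaded afresh at each visit, the set of rated regions depends on the outcome. A region with complete relief is the one most likely to be left unshaded and so to have no score. A subject whose regions have all resolved would have no VAS at all. A newly shaded region would have a follow-up score and no baseline.

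Change in VAS is an obvious summary in this study, because the VAS is the entry measure and is repeated at seven later time points. One-sample t-tests on change and repeated-measures models both need the same regions over time. The gap is hard to repair afterwards: an unshaded region may be resolved, forgotten or skipped, and setting it to zero assumes the first. With up to 25 sites, two sites could follow 7.1 in good faith and collect different data.

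**Working it through.** **The plan's own figure.** The plan gives no number on this point. Its only computed design figure is the precision in section 11.1. With n = 300 and 150 events, the exact 95% interval runs from 44.20% to 55.80%, a half-width of 5.80%, which agrees with the stated value of about 6% or less. The present point does not depend on it.

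**Which map does 7.1 mean?**

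- *For a map drawn at each visit:* the shading and the VAS are consecutive parts of one assessment; neither is restricted to baseline; and where the protocol means the baseline drawing, in 13.5.1, it calls it the baseline map, whereas 7.1 does not.
- *For the baseline map:* the areas are defined by what SCS is intended to treat, and relief does not change that intention; 13.5.1 makes the baseline map the reference for re-training; and the scale can record no pain.
- *Settled by neither:* no section requires a rating for each baseline region at each visit, and none says whether an unshaded baseline region is zero, missing or not applicable.

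The first reading is the more natural one. The second is possible.

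**Illustration 1: share of regions resolved.** The inputs are assumed, because the documents give no regional VAS data. Let q be the share of baseline regions that are fully resolved (0 cm) and unshaded, m the mean VAS over regions still shaded, and let there be no new regions.

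- Mean over all baseline regions = (1 − q) × m + q × 0 = (1 − q) × m
- Shaded-only mean ÷ all-region mean = 1 / (1 − q), whatever m is

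With m = 3.0 cm:

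| q | All baseline regions | Shaded only | Excess |
|---|---|---|---|
| 10% | 0.9 × 3.0 = 2.7 cm | 3.0 cm | 1/0.9 − 1 = 11% |
| 20% | 0.8 × 3.0 = 2.4 cm | 3.0 cm | 1/0.8 − 1 = 25% |
| 30% | 0.7 × 3.0 = 2.1 cm | 3.0 cm | 1/0.7 − 1 = 43% |

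**Illustration 2: one subject.** Assume two regions, each 7 cm at baseline; at follow-up one is resolved and the other is 4 cm.

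- Zero kept: (0 + 4)/2 = 2.0 cm, a reduction of 1 − 2/7 = 71.4%
- Region dropped: 4.0 cm, a reduction of 1 − 4/7 = 42.9%

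In general, with k regions of which r are resolved and the rest are at u cm, the two means differ by u × r/k. For 2 to 4 regions, at least one resolved and one not, and u from 2 to 5 cm, the difference runs from 2 × 1/4 = 0.5 cm to 5 × 3/4 = 3.75 cm.

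**Direction.** Dropping resolved regions raises the follow-up mean, so it understates relief. If newly shaded regions are pooled in as well, the net direction depends on their number and scores.

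**The case against.** The strongest case against is that 7.1 is ambiguous rather than wrong. A pain-free region is still one that SCS was meant to treat, it can be marked at 0 cm, and 13.5.1 states without condition that re-training uses the baseline map; the discretionary wording sits in a separate sentence about timing. The Investigator's review of the map with the subject may also catch a forgotten region. The follow-up forms are not in the documents and may already carry the baseline regions forward. The study is single-arm and descriptive with no planned hypothesis tests, and it collects pain outcomes that do not depend on the map: the PROMIS-29 pain intensity item (7.3), and PGIC and satisfaction with relief (7.2).

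Much of this stands. It shows that the baseline-region reading is possible and that the consequences are limited. It does not close the gap. Reminding a subject of the baseline map is not a requirement to rate each region on it, and the zero end of the scale helps only if the line is presented for that region. The review in 7.1 is meant to identify treated locations, not to obtain a score for each. The PROMIS item is a single rating from an instrument that is not disease-specific, whereas 13.5.1 stresses separating study pain from comorbid pain.

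**Conclusion.** The point holds as a gap in the collection rule. The documents do not fix the follow-up VAS regions to the baseline map and do not require a score for a baseline region that is no longer shaded. On the more natural reading, missing scores depend on the outcome, and change from baseline may not rest on the same regions.

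A reader might infer more than the documents support:

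- *That 7.1 limits the VAS to regions shaded at the current visit.* It does not say so; that is a reading, though the likelier one.
- *That follow-up pain will be averaged over unresolved regions only.* Section 11 defines no averaging across regions, composite or responder rule.
- *That any VAS summary will be biased, or biased in the device's favor.* Bias is conditional on the reading and on the analysis chosen, and dropping resolved regions would work against the device.

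The real size cannot be computed. The excess of 11%, 25% or 43%, and the drop from 71.4% to 42.9% relief in the two-region example, are correct arithmetic on assumed inputs: resolved regions go unshaded and are dropped, and no new regions are added. This is an improvement worth making because it is cheap and the data cannot safely be reconstructed later. It does not undermine the study.

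**What to change.** Make three changes.

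1. State in 7.1 that at every visit after baseline (Trial End and 1 to 24 months) the subject completes a VAS for each region identified as study pain on the baseline map, and marks the no-pain end (0 cm) where there is none.
2. State that newly painful regions are recorded and rated separately and are excluded from change from baseline.
3. Carry the baseline regions forward onto the follow-up form, so that a blank can be recognized as missing and is not confused with a zero.

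The cost is a sentence or two in 7.1, a form layout change and a few more seconds per visit. It needs no extra subjects or staff. If sites already work this way, the change only documents their practice.

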7.2 Patient Global Impression of Change (PGIC) and Patient Satisfaction

Patient Global Impression of Change (PGIC) is a single item measure of global improvement with treatment. The subject is presented with a 7-point rating scale containing the options “very much improved”, “much improved”, “minimally improved”, “no change”, “minimally worse”, “much worse”, and “very much worse”.

Subject recommendation of and satisfaction with the stimulation therapy and study pain relief will also be collected. Recommendation options include “strongly recommend,” “recommend,” “neutral,” “not recommend,” and “definitely not recommend.” Satisfaction options include “very satisfied,” “satisfied,” “neither satisfied nor unsatisfied,” “unsatisfied,” and “very unsatisfied.”

7.3 PROMIS-29+2

The PROMIS-29+2 consist of the PROMIS-29 profile (v2.1) and two PROMIS Cognitive Function Abilities items. The PROMIS-29 is a 29-item profile instrument that assesses 8 universal domains (not disease-specific): Physical Function, Anxiety, Depression, Fatigue, Sleep Disturbance, Ability to Participate in Social Roles and Activities, Pain Interference, and Pain Intensity. The first seven domains are assessed with 4 questions each; Pain Intensity is measured with a single 11-point numeric rating scale (NRS) from 0 (no pain) to 10 (worst imaginable pain). High scores represent more of the domain being measured. Thus, on symptom-oriented (negatively-worded) domains of PROMIS-29 (anxiety, depression, fatigue, pain interference, and sleep disturbance), higher scores represent worse symptomatology. On the function-oriented (positively-worded) domains (physical functioning and social role) higher scores represent better functioning. The addition of the two items from the PROMIS Cognitive Function Abilities, for a total of 31 questions, allows for incorporation of the PROMIS Preference Scoring System (PROPr), which is a generic societal, preference-based summary score (also called a health utility score). The PROPr is measured on scale where 0 is the utility of being dead and 1 the utility of “full health.” The lowest possible score is -0.022 (for a state viewed as worse than dead), and the highest possible score is 1.

7.4 PROMIS-10 Global

The PROMIS Global Health measure produces two scores: Physical Health and Mental Health. PROMIS Global includes 10 items: four items that reflect different aspects of physical health (e.g., fatigue, physical function, pain) contribute to a Global Physical Health score, and four items that reflect different aspects of mental health (e.g., mood, cognition, social activities/role) contribute to a Global Mental Health score. A change in Global Physical Health may be the result of a change in fatigue, physical function, or other domain of physical health. The scores present a summary of multiple aspects of health. Higher PROMIS T-score represents more of the concept being measured. Thus, a person who has T- scores of 60 for the Global Physical Health or Global Mental Health scales is one standard deviation better (more healthy) than the general population.

7.5 Profile of Mood States 2nd Edition – Adult Short (POMS 2-A Short)

The Profile of Mood States 2nd Edition – Adult Short (POMS 2-A Short) is a 35 item, 5-point Likert scale that measures mood states overall (Total Mood Disturbance) as well as for six mood clusters: Tension-Anxiety, Depression-Dejection, Anger-Hostility, Vigor-Activity, Fatigue-Inertia, and Confusion-Bewilderment. A scale score is also calculated for Friendliness, which is considered separately as a mood state that may influence the severity of the mood disturbance through interpersonal functioning. Higher scores indicate more negative mood states except for Vigor-Activity where higher scores indicate increased Vigor.

7.6 Stimulation Characteristics

Subjects will be asked questions about stimulation sensation and to shade in the areas where they typically experience stimulation sensation on a body map drawing.

7.7 Posture Change Measurements

Data on stimulation intensity and ECAP amplitude at various stimulation levels (i.e., activation plot) and in different postures will be collected in both stimulation modes. Subjects will rate the stimulation intensity on an 11-point numeric rating scale (0 equals “no feeling” and 10 equals “very intense”). All data will be recorded on device logs, except subject ratings, which will be recorded on the CRF.

7.8 Neurophysiological Measurements

Neurophysiological measurements of the stimulated fibers (e.g., ECAP features, conduction velocity, chronaxie, rheobase, late responses) will be collected. Data is automatically recorded on the device logs.

7.9 Programming Parameters and Characteristics

Program parameters (e.g., frequency, pulse width, stimulation amplitude) and characteristics (e.g., usage) will be collected. Data is automatically recorded on the device logs.

7.10 Additional Optional Assessments

Optional assessments to collect additional data may be requested that subjects can elect to participate in. Potential assessments include (but are not limited to):

- Medication interaction: Additional neurophysiological data may be collected during changes in medication to measure the effect of medications on spinal cord activation. Subjects may be requested to return to original doses of medications temporarily during this time. For example, if a subject is tapering medications, they may be asked to record their daily intake and return to the clinic for additional visits to collect neurophysiological measurements and optimize their stimulation therapy during the taper.
- Programming algorithms and dose: Various programming parameter algorithms and/or various levels of therapy or spinal cord activation “dose” may be evaluated.
- Usability: As new or modified products becomes available during the study, questions that pertain to the technical capability/performance (usability) of the product(s) may be asked of subjects.
- Pain signs/symptoms with stimulation on and/or off (e.g., Neuropathic Pain Symptom Inventory (NPSI), Complex Regional Pain Syndrome (CRPS)-specific questions, bedside-Quantitative Sensory Testing (bedside-QST))

These assessments may occur anytime during the study. These optional assessments are in addition to the required protocol data collection and there are no foreseeable additional risks to the subject. If additional testing is deemed to have additional risks, the investigator will obtain a separate consent.

Data will be collected on a CRF and/or the device log files based on the specific requirements.

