advantage of not having drug side effects, including respiratory distress, as compared to IDD systems, or addictive properties, as compared to opioid usage, which is currently of epidemic proportions in the United States (US). There is consensus among national medical societies to recommend SCS as a treatment option in patients with chronic, severe pain for which conservative treatment modalities have failed or are contraindicated(5–13). SCS may be delivered in parallel with other therapies and should be used as part of an overall multimodal treatment strategy.

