12 RISK ANALYSIS

12.1 Potential Risks

Risks associated with the Evoke System are similar to those of other open-loop SCS systems, which are generally minor. All medical procedures involve some risk of injury, including death. Other anticipated risks associated with the Evoke System are listed in this protocol or found in the literature, post-market surveillance data (e.g., FDA Manufacturer and User Facility Device Experience (MAUDE) database), and device labeling for SCS systems. Please refer to the current Evoke IFUs for the most up-to-date risks associated with the Evoke System.

In addition to the general surgical risks, potential risks to subjects associated with implantation and use of the Evoke System include, but are not limited to:

- Undesirable changes in stimulation sensation and/or location
- Uncomfortable changes in stimulation (over and/or under stimulation)
- Persistent post-surgical pain at hardware implantation sites
- CLS migration, which may result in pain or difficulty in charging
- Seroma or hematoma at surgery sites
- Epidural hemorrhage, spinal cord injury and possible paralysis
- Lead migration from the location chosen at initial implantation resulting in stimulation changes
- Breakage of the lead or failure of other system components, which may result in loss of stimulation
- Rejection of, or allergic reaction to, the implanted components
- Infection that may require hospitalization with intravenous antibiotic therapy
- Cerebrospinal fluid (CSF) leakage
- Inadequate pain relief following system implantation
- Erosion of the lead or CLS through the skin
- Weakness, clumsiness, numbness or pain

Subjects may require surgery (including revision, explant, and replacement) as a result of any of the above.

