12.3 Potential Benefits

There are several potential benefits of the Evoke System, and specifically with regard to ECAP-controlled closed-loop stimulation, to participating study subjects suffering from chronic, intractable pain of the trunk and/or limbs. These include:

- The Evoke System may provide insight into the neurophysiological mechanisms of chronic pain and SCS.
- The Evoke System may provide significant pain relief.
- The Evoke System may allow patients to reduce their pain medications.
- The Evoke System may improve patients' quality of life, sleep quality, emotional and/or physical functioning.
- The Evoke closed-loop stimulation mode may reduce variation in electrical field strengths reaching the spinal cord due to normal physiological activity and movement.
- The Evoke closed-loop stimulation mode may be more effective in providing pain relief compared to open-loop stimulation.

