13.2.2 Informed Consent

The Investigator will prepare an ICF in accordance with this study protocol, regulatory requirements (21 CFR Part 50), Good Clinical Practices (GCP), and the ethical principles that have their origin in the Declaration of Helsinki using the sample ICF provided in Appendix A of this study protocol.

As part of the consent process, the subject will have ample time and opportunity to ask questions of, and receive answers from the personnel conducting the study, and to decide whether to participate in the study. The information that is given to the subject shall be in language understandable to them.

Neither the Investigator nor the investigation site personnel shall coerce or unduly influence the subject to participate or continue to participate in the study.

All subjects must document their consent for study participation and authorization for use and disclosure of health information by signing the IRB-approved ICF. The Investigator will retain the original ICF signed by the subject and a copy of the ICF will be provided to the subject.

The Sponsor will inform the Investigator whenever information becomes available that may be relevant to the subject's consent, and will revise the ICF accordingly and provide it to the Investigator for approval by the IRB. The Investigator or his/her authorized designee shall inform the subject of this information. After approval by the IRB, a copy of this ICF must be provided to the participating subjects, and the informed consent process as described above repeated, in accordance with the IRB requirements.

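### Section 7.10 says the optional assessments add no foreseeable risk, yet one of them lets the study ask subjects to return temporarily to original medication doses, and separate consent for that is only conditional

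*Combined protocol and SAP*

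**What the plan says.** Section 7.10 of the combined protocol and SAP lists four possible optional assessments: medication interaction, programming algorithms and dose, usability, and pain signs and symptoms with stimulation on or off. The list is not meant to be complete, and subjects choose whether to take part.

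The medication-interaction item is a research measurement. Neurophysiological data are collected around medication changes "to measure the effect of medications on spinal cord activation", and "Subjects may be requested to return to original doses of medications temporarily during this time". The item's example is a subject who is tapering, who may be asked to log daily intake and come in for extra visits.

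Two general sentences about risk follow the list. The first says of the optional assessments that "there are no foreseeable additional risks to the subject". The second says: "If additional testing is deemed to have additional risks, the investigator will obtain a separate consent".

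Section 8.10 provides for medications to be recorded at baseline and changes to be tracked. Section 12.1 introduces its list with "potential risks to subjects associated with implantation and use of the Evoke System include, but are not limited to", and the items are surgical, device and stimulation risks. Section 13.2.2 has the investigator prepare the consent form in line with the protocol, "using the sample ICF provided in Appendix A of this study protocol". That appendix was not available for this review.

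**The concern.** A medication dose change that the study requests for a measurement is an intervention on the subject. Changing a dose can bring side effects of the drug, and changing it back can bring symptoms of its own. A statement that no added risk is foreseeable may be reasonable for a usability questionnaire, but it cannot be assumed for this item.

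The consequence lies in the consent step. Separate consent depends on someone deeming the testing to carry added risk, and the sentence just before it has already answered that question in the negative for the whole group. A site could follow 7.10 to the letter, ask a subject to go back to an earlier dose, and obtain no separate consent. What is at stake is whether a subject who agrees to this sub-test is told of the risk first. No estimate, sample size statement or device safety conclusion depends on it.

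**Working it through.** There is no figure to reproduce and no formula applies. The check sets the statements side by side.

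1. **What is requested.** The medication-interaction item in 7.10 allows the study to ask for a temporary return to original doses. The protocol does not define original. For a subject who has tapered, the natural reading is the dose before the taper, so the request is an increase, and because it is temporary a second change follows. For a subject whose dose has moved some other way, the direction is not stated. In every case the dose changes because the study asks for it.

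2. **Why it is requested.** The stated aim is to measure how medications affect spinal cord activation. The item also mentions optimizing stimulation during a taper, but that does not turn a requested return to an earlier dose into ordinary care.

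3. **How far the no-risk sentence reaches.** It refers to the optional assessments collectively and makes no exception. By count, 4 assessments are listed, 1 involves a requested dose change, and 0 are exempted.

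4. **What the consent sentence adds.** It is conditional. It gives no criterion for deeming risk to be present and does not say who decides. Read after the no-risk sentence, it can be taken to apply to testing beyond the listed items.

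5. **Whether another section supplies the missing statement.** Section 8.10 only tracks medications. The 12.1 list is expressly non-exhaustive but is framed around implanting and using the device, and it names no dose-change risk. Section 7.10 itself gives no drug class, dose limit, duration or monitoring for the dose return. No readable section corrects the no-risk sentence.

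6. **Whether the protocol elsewhere treats drug exposure as neutral.** It does not, but this is only background. Section 2.2 credits stimulation with the "advantage of not having drug side effects, including respiratory distress, as compared to IDD systems, or addictive properties, as compared to opioid usage", and 12.3 lists among potential benefits that "The Evoke System may allow patients to reduce their pain medications". The first compares therapies and the second is a hoped-for outcome. Neither discusses a temporary return to a subject's own earlier dose, so the point rests on steps 1 to 5.

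7. **Whether events would be missed.** Section 9.2.2 requires adverse events to be reported from consent onward. Its listed exceptions concern expected surgical effects, lack of efficacy, loss of therapy, and stimulation sensations or symptom changes handled by programming. None removes a drug side effect. No reporting gap follows.

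**The case against.** The strongest reply is that 7.10 already deals with this. Participation is elective, and the sentence after the no-risk statement requires separate consent where risk is deemed to be added. Section 13.6 makes the investigator responsible for subjects' safety and welfare, and 13.2.1 requires IRB approval of the protocol and the consent form. The original doses are ones the subject has taken before. The only worked example describes logging intake and attending visits, not a dose increase. That a site would skip separate consent is a prediction about behavior, and the consent form, which could settle the matter, cannot be seen.

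Much of this stands, and it keeps the point minor. It does not remove it. Prior use of a dose does not show that going back to it is free of added risk. The safeguards named are general, whereas the sentence at issue is specific and points the other way. The consent clause is the one safeguard aimed at this situation, and it is the one the preceding sentence weakens.

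A reader might infer four stronger things that the documents do not support:

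- **That the study plans to re-escalate opioids.** Section 7.10 names no drug class. The opioid remark in 2.2 is a general comparison of therapies.
- **That subjects are not told of the risk.** The consent form was not available, and a suitable sub-study consent may exist.
- **That adverse event data or the safety conclusions are compromised.** The reporting rules in 9.2.2 remain in force.
- **That the other three assessments are misdescribed too.** Testing different levels of stimulation, or symptoms with stimulation off, may raise its own questions, depending on whether additional means beyond the risks already accepted in the study. That was not examined here, so the fix should neither criticize those assessments nor offer fresh reassurance about them.

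**Conclusion.** The point holds for one assessment. A statement that no added risk is foreseeable is unsound when applied to a study-requested return to original medication doses, and because the consent clause is conditional, 7.10 as written could allow such a request without separate consent.

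The size is small: 1 of 4 listed assessments, optional, with general safeguards in place and no effect on any estimate. The documents give no participation rate, drug class or event rate, so the number of subjects affected cannot be estimated and none is claimed. The conclusion assumes that original doses means those taken before a taper or other change, and that the readable sections contain everything the protocol says on the matter outside the consent form. It should be corrected because the statement concerns risk to subjects and the correction is cheap.

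**What to change.** Change 7.10 only. Keep the existing no-risk sentence as it is for the other assessments, so that no new assurance is given about them, and insert after it:

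> *The preceding sentence does not apply to a medication dose change that the study requests for an optional assessment. Such a change may cause side effects of the medication, or symptoms when the dose is changed back. The investigator will obtain a separate consent before asking a subject to make it. Dose changes made in ordinary clinical care are not affected.*

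Keep the existing conditional consent sentence for all other testing.

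Do not add a dose-change item to the 12.1 list. That list concerns risks of implanting and using the device, and its closing line says that surgery may follow from any item in it, which would be wrong for a medication change. If section 12 is to mention the matter, use a separate sentence after the line on surgery.

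The cost is one amendment, approved by the sponsor and IRB under 13.10, and one short consent form for subjects who choose this sub-test. Adverse event categories, case report forms and analyses stay as they are.
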